Appendix 1.4. Details of Multiple Imputation Method to be Used in Sensitivity Analysis

For purposes of the missing data sensitivity analyses, the study duration of 30 months will be partitioned into 3 intervals of 10 months each. These will be referred to as period 1, period 2, and period 3, representing months 1-10, 10-20, and 20-30 respectively. Imputation models will be estimated and applied separately for each treatment group. Hospitalizations are not imputed for subjects after their death. The imputation procedure consists of two distinct phases: 1) models for cardiovascular-related hospitalization rates are estimated for each time interval, and 2) these models are then used to impute the number of cardiovascular hospitalizations following censoring (dropout) amongst subjects who dropout in an interval. Dropouts are the only source of missing hospitalization data, so there will be a monotone missing data pattern. The two-stage multiple imputation process developed here follows the procedure for monotone missing data in [Rubin \(1987\)](#).

Within each short time interval (10 months), a Poisson regression model with a constant rate will be assumed for hospitalization counts. No imputation is required for a patient who dies during the interval. Because the model applies only to subjects who survive the interval, and subjects who die during the interval are likely to have differing hospitalization rates, subjects who die in an interval will be excluded from the imputation model estimation. All other subjects still in the study at the beginning of the interval are included in the model estimation. The reduced exposure of dropouts during the intervals is represented by an exposure multiplier (between 0-10) of the monthly hospitalization rate ([McCullagh and Nelder, 1989](#)). The monthly hospitalization rate during the first period is a function of the baseline covariates NHYA baseline classification and TTR genotype. The monthly hospitalization rate during the second period is a function of the baseline covariates and the hospitalization counts during the first period. The monthly hospitalization rate during the third period is a function of the baseline covariates, and the hospitalization counts during the first and second periods.

PROC GENMOD will be used to compute maximum likelihood estimates (MLE) of the parameters of the Poisson regression model. It will also be used to compute the variance-covariance matrix for the estimates from each time period. A total of 1000 imputed data sets will be generated. To account for estimation error when forming the imputed data sets, 1000 independent sets of the Poisson model parameters will be generated for each time period from a multivariate normal distribution with mean equal to the MLE, and with the variance-covariance matrix equal to the MLE variance-covariance matrix. The i^{th} set of Poisson model parameters from each time period are paired together, yielding 1000 sets of parameters for generating the 1000 imputed data sets. For each iteration, the individual patient Poisson rate (λ) will be generated using the Poisson regression coefficient estimates for that iteration.

The imputation process described here is applied with each set of Poisson model parameters. Subjects without complete data are comprised of two types: those with no participation during the period, and those with partial participation during the period. For those with no participation, the prediction equation will be used to impute a hospitalization count for the entire period. For those with partial participation, the prediction model will be applied to impute a hospitalization count appropriate for the remainder of the period after the patient

dropped out. The imputed value will be added to the actual observed value for that patient from the part of the period prior to their dropping out. For example, consider a patient who drops out at month 5. The patient's Period 1 imputed value will be the sum of their actual hospitalization count from month 1 to month 5 added to the predicted value from month 5 to month 10.

Any missing data are imputed sequentially beginning with the first time period, then the second and third periods. The imputation model during the first period depends only on fully observed baseline covariates. The imputation model during the second period also depends on the hospitalization count during the first period. For any patient who dropped out during the first period, their imputed count in the first period is used in the model to produce the imputed value for that subject in period 2. Note that this differs from the process when estimating the imputation model (Rubin, 1987). A similar procedure is applied for imputation of missing values during period 3. Finally, the hospitalizations for each patient are summed to generate a complete 30-month (imputed) CV hospitalization frequency.

The null hypothesis will be tested based on the 1000 imputed data sets by computing the components of the complete-data Finkelstein-Schoenfeld statistic to yield 1000 numerator values, and 1000 denominator values (square root of the numerator variance). Following Rubin (1987), the numerators will then be averaged. The variance of this average will be the average within-imputation variance computed from the 1000 complete-data variances of the numerators combined with the between imputation variability in the numerators to yield a normal Z-statistic. The 1000 imputed hospitalization data sets will also be used to summarize hospitalization rates in the treatment groups.

Sample SAS Code

Poisson model specified below will be used to fit cardiovascular hospitalization data and will then be used to impute the missing data. The model will be fit separately for each of the 3 periods and will be done separately for both treatment groups (placebo and pooled tafamidis). Only the subjects that entered a given period (not completely missing during the period) will be used in determining the model. The "OFFSET" in the linear model implemented by PROC GENMOD is the adjustment for the exposure time in the interval (those who entered the period but did not complete the 10 months). The variable "months_exposure", used in the "OFFSET", is a log transformation of the months of exposure in a given period.

```
proc genmod data = nonmissingperiod1; ;* Only includes subjects with non-missing count data for period 1;  
class NYHAnum MUTATIONnum;  
model count = NYHAnum MUTATIONnum /dist=p link=log offset=months_exposure  
;*model terms for period1;  
output out=predpoi p=p;  
run;
```

```

proc genmod data = nonmissingperiod2; ;* Only includes subjects with non-missing count
data for period 2;
class NYHAnum MUTATIONnum;
model count = countbase1 NYHAnum MUTATIONnum /dist=p link=log
offset=months_exposure; *model terms for period 2 where countbase1 is CV hospitalization
count from period 1;
output out=predpoi p=p;
run;

```

```

proc genmod data = nonmissingperiod3;* Only includes subjects with non-missing count
data for period 3;
class NYHAnum MUTATIONnum;
model count = countbase1 countbase2 NYHAnum MUTATIONnum /dist=p link=log
offset=months_exposure; * model terms for period 3 where countbase1 and countbase2 are
CV hospitalization counts from period 1 and 2 respectively;
output out=predpoi p=p;run;

```

The macro below can be used to perform the multiple imputation. The variable “seedval” will be the starting seed and the variable “numimp” will specify the number of multiple imputations to be performed. The dataset “withmissing” will contain all the subjects that will be imputed.

```

%macro impute (output, seedval, numimp);
data &output;
set withmissing;
seed=&seedval;
do MInum = 1 to &numimp;
lambda= exp( $\pm$  x.xx  $\pm$  x.xxx countbase(varies depending on the period)  $\pm$  x.xx *NYHAnum
 $\pm$  x.xx*MUTATIONnum);
count = ranpoi(seed, lambda); * coefficients will be randomly generated from a normal
distribution based on the estimates and standard error output from PROC GENMOD;
output;
end;
run;
%mend impute;

```

The macro input statement will use a seed value of 999 and perform 1000 multiple imputations.

```

%impute (impute2, 999, 1000);

```

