Subjects should be instructed not to take more than 4 capsules when taking their daily blinded therapy. It should also be noted that at Month 6 and Month 12 visits, dosing should take place 7 hours (± 2.5 hours) prior to the timing of PK sample. On the day prior to Month 6 and Month 12 visits, subjects are permitted to take their usual AM dose and then take the next day's dose in the PM if necessary to adhere to the PK sampling schedule.

In the event that subjects experience adverse events that may be associated with the tolerability of treatment with tafamidis that may impact dosing adherence, they should return to the clinic with their medication. If the investigator assesses that the tolerability issue is persistent and anticipated to impact dosing adherence and that the subject's safety is not compromised by continuing treatment, then the subject may receive blinded treatment re-assignment and potential dose reduction.

Prior to blinded dose reduction, the site should collect a PK sample, noting the actual time of last dosing and the actual time of PK sample collection. The site personnel will enter the subject's study-specific identification (SSID) number into the IRT system and request blinded dose reduction. The IRT system will provide a new container number for blinded treatment re-assignment for this subject. If the subject was receiving the 80 mg dose, then the re-assignment will be to 40 mg. If subject was receiving placebo or the 20 mg dose, they will be maintained on that dose but will still receive a new container number in order to maintain the blind. If poor tolerability continues following the blinded re-assignment, the site has the option to discontinue dosing for this subject and to terminate study participation. In the event of early study discontinuation, the site staff will follow-up on the subject's vital status / transplant status 30 months after randomization.

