The term “censored” refers to a subject who discontinues from the trial for reasons other than death. For such subjects, there will be additional follow-up to obtain vital status (and transplant / cardiac mechanical assist device status) at Month 30 and that information will be used in the analysis. In the case where one subject is censored before a second subject has died, and where the vital status of the first subject at Month 30 is missing, then the frequency of cardiovascular-related hospitalizations at the shorter of their follow-up times (the shorter of the 2 subjects’ study participation) will be used in assigning a +1 or -1. In the simpler case

where one subject drops out but both are known to be alive at Month 30, the frequency of cardiovascular-related hospitalizations, at the shorter of their follow-up times (the shorter of the 2 subjects study participation), will be used in assigning a +1 or -1. Comparisons of cardiovascular related hospitalization frequency for subjects who completed all 30 months study duration will be based on the earlier of the two actual study durations (days).

Subjects, who discontinue for transplantation (ie, heart transplantation and combined heart and liver transplantation) or for implantation of a cardiac mechanical assist device, will be handled in the primary analysis in the same manner as death. More specifically, the time of the transplant or cardiac mechanical assist device implant will be used in the subject-to-subject comparison in the same manner as if the subject had died at that time (regardless of any additional vital status follow-up information). Data from subjects who drop out for a liver-only transplantation will be handled in the same manner as the data from all other censored subjects.

To examine the potential effect of including heart transplantation or cardiac mechanical assist device as “deaths” in the primary analysis, a sensitivity analysis will be performed treating all transplantation or cardiac mechanical assist device in the same manner as any other censored observation.

As an additional sensitivity analysis, a multiple imputation analysis will be applied using the method developed by Rubin (Rubin 1987). Combined results will be provided for the primary analysis (ie, using Finkelstein-Schoenfeld) as well as for the separate mortality and morbidity elements. Details are provided in the SAP.

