7. HANDLING OF MISSING VALUES

No imputation will be done for missing cases for the primary analysis based on the Finkelstein-Schoenfeld method. A sensitivity analysis (of the primary) using multiple imputation as described in [Appendix 1.4](#) will be performed. Supplemental analyses of the two key secondary variables will group the subjects on the basis of their dropout or missing-data patterns using a pattern mixture model described in [Section 8.2.2](#). For all analyses using mixed model repeated measures, no imputation of missing values will be done.

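### The planned imputation of hospitalisations after dropout does not test loss of benefit once tafamidis subjects leave the study, and no other planned analysis of the primary endpoint does

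*SAP*

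**What the plan says.** **Primary analysis.** SAP Section 7 states: "No imputation will be done for missing cases for the primary analysis based on the Finkelstein-Schoenfeld method". Under Protocol 9.2.1 and SAP 8.1.1, pairs not separated on mortality are compared on cardiovascular hospitalisations up to the shorter of their two follow-up times.

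**Imputation.** Appendix 1.4 splits the 30 months into three 10-month periods and fits a Poisson model in each. On arms it says: "Imputation models will be estimated and applied separately for each treatment group". Its sample-code text names the two groups as placebo and pooled tafamidis. Subjects who die in a period are left out of that period's fit; otherwise, "All other subjects still in the study at the beginning of the interval are included in the model estimation". The predictors are NYHA class, genotype and earlier counts; for example, "The monthly hospitalization rate during the second period is a function of the baseline covariates and the hospitalization counts during the first period". The appendix also says: "Dropouts are the only source of missing hospitalization data".

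**Leaving the study.** Protocol 5.5 says that if poor tolerability continues after blinded re-assignment, "the site has the option to discontinue dosing for this subject and to terminate study participation". Protocol 6.3.1 likewise ends both study drug and participation at transplant or device implantation. For subjects who leave, Protocol 9.2.1 says "there will be additional follow-up to obtain vital status (and transplant / cardiac mechanical assist device status) at Month 30". It makes no matching provision for hospitalisations.

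**Other checks on the primary.** SAP 8.2 and 8.2.4 plan a per-protocol repeat, exclusion of indeterminate hospitalisations, censoring at transplant or device, an added region stratum, and analyses by dose and subgroup. None concerns missing hospitalisation counts.

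**The concern.** Because stopping drug generally coincides with leaving the study, the data used to fit the tafamidis model come essentially from treated time. No covariate lets the rate change at exit. Every imputed month for a tafamidis dropout therefore carries the tafamidis in-study rate, given that subject's NYHA class, genotype and earlier counts.

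The question a reader would most want answered is whether the result survives if dropouts lose the benefit once they stop. This analysis assumes that away. The SAP plans pattern-mixture analyses for the two key secondary endpoints (Section 8.2.2), but gives the primary endpoint no reference-based, delta or tipping-point analysis. At stake is how much reassurance can be drawn when the imputed result agrees with the primary.

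**Working it through.** **Inputs from Protocol 9.1.** 160 placebo and 240 pooled tafamidis; 30-month mortality 25% against 17.5%; cardiovascular hospitalisations 2.5 against 1.5, read as means over 30 months; two-sided alpha 0.05. The stated powers are 96% (50% mortality reduction, N=300), 80% (30% reduction, N=300) and 90% (30% reduction, N=400).

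**Assumptions not in the documents.** Dropout of 10% to 40% per arm, the rate after exit, over-dispersed (gamma-Poisson) counts with shape 0.8, NYHA III in 35% and variant genotype in 30% with no prognostic effect, and vital status known for everyone.

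**Step 1: reproduce the plan's figures.** I simulated the Finkelstein-Schoenfeld test T/√V, unstratified, with 10,000 trials per case. Plain Poisson counts give 100%, 99.8% and 100%, which does not match. Gamma-Poisson counts with shape 0.8 give 95.7%, 79.9% and 90.1%, against the stated 96%, 80% and 90%.

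**Step 2: rough size in counts.** The credit per randomised tafamidis subject is dropout × share of follow-up missed × (2.5 − 1.5). With half the follow-up missed:
- 10% dropout: 0.10 × 0.5 × 1.0 = 0.05
- 25% dropout: 0.25 × 0.5 × 1.0 = 0.125
- 40% dropout: 0.40 × 0.5 × 1.0 = 0.20

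These ignore deaths after exit, after which nothing is imputed, so they are on the high side.

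**Step 3: run Appendix 1.4 as its text describes.** Three Poisson fits per arm, parameter draws and Rubin combination, with 20 imputations rather than 1000 and 700 trials per scenario. Entries are mean Z, with the percentage of trials significant.

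| Scenario (dropout) | Full data | Primary | Appendix 1.4 | Placebo model for tafamidis dropouts |
|---|---|---|---|---|
| Effect lost after exit, 10% | 3.09 (87%) | 3.18 (88%) | 3.22 (88%) | 3.12 (88%) |
| Effect lost, 20% | 3.03 (87%) | 3.17 (89%) | 3.26 (90%) | 3.07 (88%) |
| Effect lost, 30% | 2.92 (83%) | 3.13 (87%) | 3.27 (90%) | 2.97 (85%) |
| Effect lost, 40% | 2.79 (78%) | 3.06 (85%) | 3.26 (89%) | 2.86 (81%) |
| Effect persists, 30% | 3.34 (93%) | 3.22 (89%) | 3.36 (92%) | 3.05 (89%) |
| No effect, equal non-informative 30% | 0.00 (2.9%) | 0.02 (3.7%) | 0.00 (3.9%) | 0.01 (2.6%) |

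Where the effect is lost, Appendix 1.4 minus full data is:
- 10%: 3.22 − 3.09 = 0.13
- 20%: 3.26 − 3.03 = 0.23
- 30%: 3.27 − 2.92 = 0.35
- 40%: 3.26 − 2.79 = 0.47

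Appendix 1.4 minus primary is 0.04, 0.09, 0.14 and 0.20. The placebo-model run exceeds full data by 0.03, 0.04, 0.05 and 0.07; it does well here because its assumption matches the scenario. Monte Carlo error on power is about 1.2 points.

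**Step 4: further checks.** A second simulation of the 30% scenario with the effect lost gave 3.01 (full data), 3.19 (primary), 3.35 (Appendix 1.4) and 3.05 (placebo model). In about a quarter of its trials the imputed Z was below the primary Z. With no effect but frailty-driven dropout of 40% on tafamidis and 10% on placebo, the mean Z values were −0.07, 0.23, 0.35 and 0.24 in the same order. Appendix 1.4 was significant in 5.4% of those trials.

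**The case against.** A reader might infer three stronger things, and the documents do not support them.

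*That the analysis cannot challenge the primary, or only repeats its assumption.* The primary imputes nothing and truncates each comparison. Appendix 1.4 rebuilds 30-month counts, conditions on each subject's own earlier hospitalisations, and adds between-imputation variance. It therefore tests truncation and dropout related to observed history, and its Z can fall below the primary's in a single trial.

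*That it favours tafamidis by construction.* The lean is conditional. It needs a real effect that fades after exit, or sicker subjects leaving tafamidis more often. The documents give no post-exit hospitalisation rate, and Protocol 1.2.3 hypothesises a disease-modifying therapy, so full reversion to the placebo rate is one assumption among several.

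*That it uses only subjects who stayed on drug.* The fitting set is defined by being in the study. It includes those who drop out during a period, with reduced exposure.

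Two limits on size also stand. Mortality ranks first, and Month 30 vital status is sought for dropouts, so loss of survival benefit is largely observed; only the second tier is imputed. The analysis also sits under exploratory analyses, with no decision rule attached. What remains is the gap itself: nothing planned for the primary varies the rate after exit.

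**Conclusion.** The point holds as a limitation of a sensitivity analysis. Appendix 1.4 assumes tafamidis dropouts keep their arm's in-study rate, and no planned analysis of the primary tests the alternative.

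If a real hospitalisation effect is lost after exit, the planned imputation overstates the full-data mean Z by about 0.13 to 0.47 at 10% to 40% dropout. On average it then lies further from the full-data value than the primary does. At 10% to 20% dropout the consequence is small: 88% against 87%, and 90% against 87%, of trials significant. With a persisting effect (3.36 against 3.34), or no effect and equal non-informative dropout (0.00), it does not lean.

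These sizes rest on the assumed dropout, dispersion and reversion to the placebo rate. They do not show that the trial's result is biased.

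**What to change.** Keep the Appendix 1.4 run and state its assumption: after exit, dropouts keep the in-study rate of their own arm. Before unblinding, add a second run in which tafamidis dropouts' post-exit counts are drawn from the fitted placebo models, with the same periods, covariates and 1000 draws. Report both as a range of assumptions. The second run should not be a pass/fail gate for robustness, since that would replace one untested assumption with another.

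In both runs, scale the draw by the months remaining in the period. The text of Appendix 1.4 requires this, but its sample macro draws from a rate with no such multiplier although the models are fitted with a log-months offset. Run literally, the macro would impute about one month of events per period.

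The cost is a little more programming, because the placebo models are already fitted. The second result is conservative if benefit persists after stopping: mean Z about 3.05 against 3.34 with full data at 30% dropout, a shortfall of 0.29. It also does not remove the distortion from frailty-driven unequal dropout (0.24 against −0.07 with full data).

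### In SAP Appendix 1.4 the sample imputation macro multiplies CLASS-level coefficients by raw numeric codes, which taken literally inverts the fitted NYHA and genotype rate ratios.

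*SAP*

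**What the plan says.** SAP Appendix 1.4 splits the 30 months into three 10-month periods and imputes cardiovascular hospitalizations after dropout from Poisson models. The first-period rate is a "function of the baseline covariates NHYA baseline classification and TTR genotype". The second and third periods add earlier hospitalization counts. On arms it says: "Imputation models will be estimated and applied separately for each treatment group". On volume: "A total of 1000 imputed data sets will be generated".

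Each of the three sample PROC GENMOD calls carries "class NYHAnum MUTATIONnum", with no option for parameterization, reference level or level order. The prose says that each patient's rate "will be generated using the Poisson regression coefficient estimates for that iteration". It does not say how the two covariates are coded.

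The macro is introduced with "The macro below can be used to perform the multiple imputation". Its rate line is the exponential of an intercept, a term for the earlier count, a coefficient times NYHAnum, and "x.xx*MUTATIONnum". A comment says that the coefficients come from a normal "distribution based on the estimates and standard error output from PROC GENMOD".

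**The concern.** A CLASS coefficient is a shift that belongs to one level. It is not a slope on the numeric code. Multiplying it by the code is right only if the level that owns the coefficient is coded 1 and the reference is coded 0. Under default ordering of unformatted numeric codes, the level coded 1 in a 0/1 variable is the reference, so the requirement fails.

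This is the one missing-data sensitivity analysis that the SAP plans for the primary analysis (Sections 7 and 8.2.4). Its data sets also supply hospitalization-rate summaries by arm. If the code were followed as printed, dropouts would receive rates from the wrong risk level or rates on the wrong scale. A first-period error would also carry forward, because imputed counts feed the later-period models. Since the models are fitted by arm, the distortion differs between arms wherever the covariate effects do.

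**Working it through.** The plan gives no imputed rate, covariate rate ratio or numeric coding, so there is no figure of its own to reproduce.

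**Inputs**
- Fitting and prediction steps: SAP Appendix 1.4, as above. Default CLASS coding (last ordered level is the reference, with coefficient 0) is standard SAS behavior and is not stated in the documents.
- NYHA III share 24%: the TRACS figure for class III or higher, 7/29 (Protocol Section 1.2.1). Variant share 30%: the enrollment floor (Protocol Section 3). Independence of the two is assumed.
- Rate ratios (NYHA III v I/II, variant v wild-type): assumed.
- Codes: assumed 0/1 or 1/2.

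**Algebra.** Take one covariate with codes c1 < c2, intercept a and coefficient b.
- Fitted rates: exp(a + b) at c1 and exp(a) at c2.
- Macro rates: exp(a + b·c1) and exp(a + b·c2).
- For b ≠ 0 these agree only if c1 = 1 and c2 = 0, which contradicts c1 < c2.
- First-to-last rate ratio: exp(b) fitted, exp(b(c1 − c2)) = exp(−b) from the macro for adjacent integer codes. The ratio is inverted.

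With 0/1 codes the two levels exchange rates, whichever carries the higher risk. With 1/2 codes the first level is right and the second is multiplied by exp(2b). That is 1/RR² if the higher-risk level is last (0.64 at RR 1.25, 0.44 at 1.5, 0.25 at 2.0) and RR² if it is first (4 at RR 2.0). Earlier-period counts are not CLASS variables, so their slopes are used correctly.

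**Check on a fitted model.** A Poisson model with last-level-reference dummies was fitted to simulated data (ratios 2.0 and 1.5, 0/1 codes). The low/low cell was fitted at 0.554 per 10 months and the macro gave 1.667. The high/high cell was fitted at 1.667 and the macro gave 0.554. With CLASS removed, macro and fit agreed in all four cells (ratio 1.000).

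**Mean imputed rate relative to the fitted rate** (ratios 2.0 and 1.25; I/II wild-type = 1)
- Fitted: (0.76 + 0.24×2.0) × (0.70 + 0.30×1.25) = 1.24 × 1.075 = 1.333.
- 0/1: (0.76×2.0 + 0.24) × (0.70×1.25 + 0.30) = 1.76 × 1.175 = 2.068; 2.068/1.333 = **1.55**.
- 1/2, higher risk last: (0.76 + 0.24×0.5) × (0.70 + 0.30×0.8) = 0.88 × 0.94 = 0.827; 0.827/1.333 = **0.62**.
- 1/2, higher risk first: (0.24×2.0 + 0.76×4) × (0.30×1.25 + 0.70×1.5625) = 3.52 × 1.469 = 5.17; 5.17/1.333 = **3.9**.
- Milder case, NYHA ratio 1.5 and no genotype effect: 1.38/1.12 = 1.23 (0/1) and 0.92/1.12 = 0.82 (1/2, higher risk last).

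**Effects that differ by arm** (NYHA ratio 2.0 on placebo and 1.2 on tafamidis, no genotype effect)
- 0/1: placebo 1.76/1.24 = 1.42; tafamidis (0.76×1.2 + 0.24)/1.048 = 1.10; 1.42/1.10 = 1.29. Placebo is overstated by about 29% relative to tafamidis.
- 1/2, higher risk last: placebo 0.88/1.24 = 0.71; tafamidis (0.76 + 0.24/1.2)/1.048 = 0.92. With unrounded values 0.710/0.916 = 0.775, about 22% the other way.

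**Effect on the stratified Finkelstein-Schoenfeld Z** (small simulations, N = 400, exposure term restored)
- Same covariate effects and dropout in both arms, 10% to 40% dropout, 60 replicates: mean Z moved by at most about 0.1. At 40% dropout with ratios 2.0 and 1.5 it was 2.97 correct, 3.04 with 0/1 and 2.87 with 1/2. The mean imputed count per dropout moved more: 0.95 correct, 1.43 and 0.48.
- Unequal arms, 0/1 codes, 150 replicates. NYHA ratio 2.0 on placebo and 1.2 on tafamidis with 30% dropout: mean Z 3.61 became 4.11. No treatment effect with 40% placebo and 20% tafamidis dropout: 0.03 became 0.52. With 1/2 codes the shift was about 0.1 in the opposite direction.

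**The case against.** The strongest reply is that this is a template. The macro is offered as something that can be used, its coefficients are placeholders, and the rate line cannot run as printed. A programmer must rewrite it, and the prose asks for the right thing, a rate from the fitted model. Each GENMOD call also writes out predicted values, so validation could expose a mismatch. This stands as a limit on the claim: the documents do not show that any imputed rate will be wrong. It does not remove the inconsistency, because the prose never states the coding and nothing requires the comparison.

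A second reply is that formats could rescue the formula. If code 0 were formatted as wild-type and code 1 as variant, wild-type would sort last and become the reference, and the genotype term would be right. That is correct, so the algebra covers unformatted codes only. The SAP specifies no format.

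Third, the comparison is made within NYHA-by-genotype strata, so exchanging rates between strata does not change who is compared with whom. This also stands, and it explains the small movement in Z when the arms behave alike.

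A reader might infer that the error favors tafamidis. The documents do not support that: under the same assumed ratios the sign reverses with the codes. A reader might also infer a several-fold shrinkage of rates. That needs 1/2 codes, the higher-risk level last and a large ratio. At a ratio of 1.25 on one covariate the second level is cut 1.6-fold, and with the order reversed rates are inflated.

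**Conclusion.** The fitting step and the prediction step in the sample code are inconsistent. Under default SAS coding and unformatted numeric codes, following both literally inverts the fitted NYHA and genotype rate ratios. That conclusion is algebraic.

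The size and direction are not determined by the documents. The illustrations above rest on assumed codes, rate ratios, shares and independence. The effect on the tested statistic is small when covariate effects and dropout are alike across arms. It reached about 0.5 in Z only in the assumed unequal-arm cases with 0/1 codes.

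The primary analysis uses no imputation (SAP Section 7) and is unaffected. The reach is dropouts' imputed counts in the sensitivity analysis and the imputed rate summaries by arm, which are the more exposed of the two.

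Two other features of the macro are separate and should not be counted here: its rate line has no exposure term, and its comment describes draws from standard errors where the prose specifies the full covariance matrix.

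**What to change.** In all three GENMOD models of Appendix 1.4, do one of the following:
- drop the CLASS statement and enter 0/1 indicators (NYHA III = 1, variant = 1) as numeric terms; or
- keep CLASS with PARAM=REF REF=FIRST and unformatted 0/1 codes.

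With either, the covariate terms in the macro are right as they stand. State the coding in the appendix. Add one check: the macro's rate at the maximum likelihood estimates, with the exposure term included, must reproduce the GENMOD predicted values for the modeled subjects.

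The cost is a few words of code, one sentence and one check, with no change to data or design. The SAP describes the study as ongoing and blinded (Section 1), so the correction can be made before unblinding.
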